**Table 6. Modules included in provider survey**

Module	Topic	Description
1	Background and demographic characteristics	Factors such as age, education, prior experience, etc., have influences on worker performance and ability to deliver services.
2	Workload and time commitment (both actual and perceived)	Information on workload and time commitments are needed for three purposes: 1) to understand demands made by project interventions on workload and time commitments; 2) to understand how perceptions of workload, in addition to actual workload, influence FHW motivation and performance; 3) to use data on time commitments, and shifts in time commitments and activities due to the interventions; and 4) additional and different workload and time commitments due to COVID-19.
3	Training exposure and needs assessment for future training	To effectively deliver the MIYCN service delivery package, providers require training to develop their competency in performing required duties. In addition, training is known to be a motivating influence on health providers. Training was also required to adapt and continue the implementation of the MIYCN service delivery package during COVID-19.
4	Knowledge and skills related to MIYCN	A basic prerequisite for delivering the MIYCN intervention successfully is knowledge of providers about the core topics of MIYCN. Additional knowledge and skills were required during COVID-19.
5	Self-efficacy and confidence	Self-efficacy and confidence is a basic driver of job motivation and job performance during normal circumstances and during COVID-19.
6	Job motivation and satisfaction	Several factors influence provider motivation. These include factors that are extrinsic to the provider as well as intrinsic motivators. Motivation is strongly related to job performance; therefore, capturing perceptions related to motivation and motivators is important both at the baseline and endline. Job satisfaction is also an influence on job performance, and therefore important to capture. COVID-19 will also influence job motivation and satisfaction.
7	Supervisory support	Supportive supervision is documented to be critical in provider performance, motivation, and training during normal circumstances and during COVID-19.
8	Incentives and remuneration	Incentives and remuneration influences motivation and performance of providers during normal circumstances and during COVID-19.

### 9.3. Case observation

Case observations will be conducted in both intervention and comparison health facilities at baseline and endline. The observation checklists will be used to observe the service content as well as interactions between the client and provider. Specifically, the counseling observation checklist will be developed based on the MIYCN service delivery package guidelines. In addition to content coverage, a checklist will also be used to assess counselors' skills and counseling processes. Items from this checklist will be used to measure the quality of the counseling session. At the end of the counseling session, a short exit interview (5-10 minutes) will be used, to ask the respondents about services received during that visit, nutrition information provided, and their satisfaction with the services they received

At baseline, 1400 case observations (1200 in intervention and 200 in control groups) were conducted, along with basic client information. During the facility-based endline, 1200 case observations will be conducted in each group. We expect to have 15 days of observations in each facility, 10 observations per day: 5 ANC visits (include counseling), 5 child or immunization visits (include counseling). Total:  $10*15 \text{ days}*8 \text{ facilities}=1200$  observations in interventions and 1200 in comparison facilities.

### 9.4. Client interview

Clients who are observed at facilities will also be interviewed in their homes as a follow-up to measure behavior change (**Table 7**). During the facility interviews, we will seek their consent for the community interview to contact them to set up home visit within one month. We expect that we will be able to follow 65-70% of these women. By doing so, we ensure that our clients will have at least one visit in the evaluation facilities (both intervention and control areas). We can track the number of facilities visits and thus conduct the dose response analysis.

**Table 7. Modules included in client interview**

Module	Topic	Description
1	Background and demographic characteristics	Factors such as age, education, religion, living standard, etc., have influences on client's behaviors, including MIYCN practices and service utilization. This data also provides information about outside factors, including the COVID-19 pandemic that may constrain mothers' ability to benefit from services. Data will be collected on household information, socioeconomic status, income and expenditure, and the education and other characteristics of the women and their husbands.
2	Obstetric history	This section information on the woman's pregnancy history including complications, total parity and age at first parity.
3	Previous ANC care/care seeking for the child	This will include receipt and consumption of IFA and calcium and antenatal care and counselling during current pregnancy for pregnant women. Mothers of sick children will also be asked about postnatal services, morbidity and care of children, and vaccination history. This will help to assess if exposure to

Module	Topic	Description
		intended program is occurring as expected and assess impact trends by levels of exposure to interventions.
4	MN Dietary intake/IYCF practices	Respondents will be asked to recall what they ate (ANC clients) or what they fed their children (mothers of sick children) on the previous day. Mothers of sick children will also be asked other questions on IYCF practices and behaviors. This will provide information on MIYCN behaviors.
5	Current MIYCN knowledge and perceptions	Data on mothers' MIYCN knowledge and perceptions can be used to assess trends in impact indicators and to identify pathways to positive behavior change. Questions on self-efficacy will be included.
6	Social desirability	This is a factor that may affect the woman's ability to change behaviors and practices around MIYCN.
7	Food security	Questions on food security will be included as they are related to the respondent's ability to follow counselling on diet for herself and her children.
8	Decision-making power and mental health	Decision-making power and mental health are also related to the woman's ability to change behaviors and practices around MIYCN.
9	Current MIYCN knowledge and practices	Follow-up data on mothers' MIYCN knowledge and practices can be used to identify the impact of the intervention in terms of promoting behavior change. For data comparability, the same tools will be used for this round of data collection.

## 9.5. Program Manager and Field Supervisor interviews

In-depth interviews will be conducted using a qualitative interview guide. The interview guide will be developed in English and then translated into Bengali (if needed). These tools will be pretested for clarity, flow, and priority questions (to cover all domains with the least number of questions) and modified accordingly. The in-depth interviews will be conducted in English or Bengali by skilled and trained research assistants with accompanying researchers. Audio recordings will be transcribed (and independently translated into English, if needed) and compared to the original as a quality check.

## 9.6. COVID-19 precautionary measures

Since early 2020, close-range contacts between enumerators and study participants during data collection activities present a particular risk for spreading COVID-19 in communities with vulnerable populations. The collaborating survey firm, Data Analysis and Technical Assistance (DATA) has developed formal guidelines to be followed during enumerator training and fieldwork. As part of the guidelines, all study staff will be tested for COVID-19 before enumerator training begins. Any individual who tests positive will be excluded from the training and advised to isolate and seek appropriate health services as per government and local guidelines. Before each day of training, participants will be screened for COVID-19-related symptoms (fever, dry cough, respiratory problems, or any unusual illness). If any participant presents symptoms, they will be advised to take a COVID-19 test and may only rejoin training after presenting a negative test result. All

participants must wear face masks (provided to them) throughout the duration of training. During data collection, field supervisors will assess enumerators for COVID-19 symptoms each day before starting data collection and tested twice (once per month of data collection). As with training, any enumerator or staff who tests positive or presents symptoms will be immediately excluded from fieldwork and must present a negative COVID-19 test result before rejoining fieldwork. Any study participants with COVID-19 symptoms will be excluded from the study and advised to isolate and seek appropriate health services as described above. All enumerators and study participants will wear masks (provided to them) and wash or sanitize their hands before and after each interview. Interviews will be conducted outside or in a well-ventilated space and enumerators will maintain two meters of distance from the interviewee and other household members.

Co- and Principal Investigators of the project will be in daily contact with DATA and in-country partners during data collection to assess the changing risks and government measures.

## 10. Analysis plan

All statistical analysis using quantitative data will be done using Stata 17. Data collected at baseline will be analysed to examine the balance on key baseline characteristics between intervention and comparison groups. Statistical testing for differences between the two groups will be done using a random effects regression, taking into account the clustering of errors within and across health facilities.

Appropriate variables will be created for each set of outcomes. For quality of care, the key indicators will be facility readiness, knowledge of healthcare providers, nutrition counselling service scores, and clients' utilization of and satisfaction with MIYCN services. For behaviour outcomes, the key indicators will be maternal nutrition practices (dietary diversity, IFA and calcium consumption) and age-appropriate IYCF practices. Impacts on these outcomes will be estimated using analysis of covariance which is an accepted impact evaluation analysis approach that is widely used. Further adjustment for geographic clustering at the facility level will be done using random effects.

Qualitative interview data (transcripts) will be organized and analyzed using software such as NVivo, Excel or others as appropriate. Data analysis will identify the emerging deductive and inductive themes that emerge from the interviews under 4 study domains: intervention impact pathway, uptake of interventions, programmatic performance, and supportive supervision activities. Categories and subcategories under these domains will be identified and defined (conceptualized) to feed into a narrative complementing the quantitative data results.

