## 7. Sample size and power calculation

Sample size has been estimated based on the baseline prevalence of the primary outcomes, the expected change after intervention, the power to detect those differences at 0.80, and a level of significance of 0.05. The outcomes used for sample size calculation were quality of nutrition service delivery (including provision of counseling on diet and breastfeeding practices). The sample size was calculated at 2 levels: provision of services (measured through case observation) and receipt of services (measured through client interviews).

Based on data from baseline assessment, we calculated the prevalence for expected outcomes, and the intra-cluster correlations (ICCs). We estimated that a minimum sample size of 1200 clients per group during the first phase of the endline survey conducted at the facilities would have at least 80 percent power to detect a difference of 10-19 percentage points (pp) between intervention and comparison groups in the changes over time for different context-specific outcomes (**Table 2**), e.g. maternal counselling during pregnancy and IYCF counselling to caregivers of young children. During the follow up in the communities, we expect a ~30-33% loss from the original sample, and thus estimate we will collect information from 65-70%. We expect that this will give us enough power to detect changes in context-specific behavioral outcomes. Instead of separating the sample for ANC and child contacts, we will pool them to examine context-appropriate behavior such as pregnant women with dietary diversity/IFA and calcium consumption and caregivers with age-appropriate child feedings. These detectable differences are of reasonable public health significance and based on the previous experience from evaluation of the A&T Bangladesh maternal nutrition study [7].

For facility readiness and provider knowledge, with the sample size of 8 facilities and 40-64 providers in this group, we will mainly report the descriptive analyses between two groups, but not report statistical test due to small sample size.

Table 2. Sample size and power calculation

	Control group, endline 	Expected difference	Treatment group, endline	Power	ICC	Alpha	Sample size per group
Quality of services (measured through case observation)							1200
Counseling on diet	68.0	19.0	87.0	0.8	0.103	5	
Counseling on breastfeeding	71.6	17.1	88.7	0.8	0.09	5	

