Context-appropriate behavioral outcomes (measured through client interview)							1200 at facility-based endline 800 (67%) at community-based endline
Consume 100+ IFA	54.5	9.5	64.0	0.8	0.001	5	
Dietary diversity during pregnancy	74.0	9.5	83.5	0.8	0.009	5	
Early initiation of breastfeeding	32.8	13.5	46.3	0.8	0.024	5	

Data from AINNS study [8]

Data from Bangladesh DHS 2014 [9]

We expect to see no difference in the control group at baseline vs. endline.

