## 8. Sampling and enrollment of study subjects

**Sampling providers:** The program interventions are implemented in 8 NGO-run health facilities in Dhaka, with another 8 serving as comparison facilities; thus, 16 facilities will be included in the survey. From each facility, we will interview 6-8 health providers (1 medical officer or 1 paramedic, 1-2 counselors, and 3-4 community workers) (**Table 3**). We expect that the number of counselors across facilities may differ; counselors may already be present at some intervention and comparison facilities prior to the intervention. Therefore, 1 counselor may be interviewed at comparison facilities, and 1-2 counselors (1 existing counsellor and 1 additional A&T MIYCN Counselor) may be interviewed at intervention facilities. Similarly, dedicated Community Workers hired by A&T will be available at intervention facilities but not at comparison facilities. Due to the small numbers of Program Managers (n=2) and Field Supervisors (n=4), we plan to conduct in-depth interviews with them to obtain some additional insights on overall intervention impact pathway, uptake of interventions, program performance and supportive supervision activities.

Table 3. Sampling healthcare personnel at intervention and comparison facilities

Levels		Intervention facilities (n=8)	Comparison facilities (n=8)
Baseline	Permanent facility personnel		
	Medical officer	1	1
	Counsellor	1	1
	Paramedic	1	1
	Community worker	3	3
	Total:	N=48	N=48
Endline: Quantitative survey	Permanent facility personnel		
	Medical officer	1	1
	Counsellor	1	1
	Paramedic	1	1
	Community worker	3	3
	A&T temporary hiring		
	MIYCN Counsellor	1	0
	Community Worker	1	0
	Total:	N=64	N= 48
Endline: Qualitative in-depth interview	Program Manager	2	0
	Field Supervisor	4	0
	Total:	N=6	N=0

**Sampling clients:** At each health facility, 4 intervals of time (8-10 AM, 10AM-12PM, 1-3 PM and 3-5 PM) will be chosen. Pregnant women or children visiting the facility within these 4 selected intervals will be randomly selected (in proportion to the case load in each interval) for interview and observation. We plan to sample 10 clients each day from each facility (5 pregnant women and 5 mothers with children <12 months).

The inclusion criteria for recruiting clients are as follows:

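### On Table 2's unadjusted inputs, the two counselling-quality rows have about 75% power rather than 80% once the 5% test uses the 14 facility degrees of freedom, and section 10 states no df rule

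*Combined protocol and SAP*

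**What the plan says.** Section 7 sets "the power to detect those differences at 0.80, and a level of significance of 0.05", and states that 1200 clients per group "would have at least 80 percent power to detect a difference of 10-19 percentage points (pp) between intervention and comparison groups". That sentence goes on to describe the difference as one in changes over time. Table 2, however, lists endline percentages only, and its footnote 3 assumes no change in the control group, so the contrast it sizes is an endline difference.

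Section 8 fixes the number of clusters: "thus, 16 facilities will be included in the survey", 8 per group. Section 9.3 fixes the cluster size: "We expect to have 15 days of observations in each facility, 10 observations per day", or 150 per facility and 1200 per group.

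On the analysis, section 10 says "Impacts on these outcomes will be estimated using analysis of covariance" and then "Further adjustment for geographic clustering at the facility level will be done using random effects". It names the software, but no estimator, reference distribution, df rule or small-sample correction. Section 7 withholds significance tests on grounds of small sample size only for facility readiness and provider knowledge. The client-level outcomes will therefore be tested, on the same 16 facilities.

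**The concern.** Counselling quality is a primary outcome (section 4), and its two Table 2 rows are the more heavily clustered basis for the sample size. When nearly all the variance of the group contrast lies between facilities, the test has about as many degrees of freedom as there are facilities less two, however many clients are observed. A power figure taken from the normal distribution then promises more than a test that holds 5% can deliver. Because section 10 does not fix the reference distribution, a reader cannot tell which error will occur: lower power than stated, or a false-positive rate above the stated 5%.

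**Working it through.** **Inputs.** Percentages, differences and ICCs from Table 2; 8 facilities per group (section 8); 150 observations per facility (section 9.3). Assumptions: equal cluster sizes, and a two-sided test. Sidedness is not stated, but a one-sided 5% normal test gives about 87% and so does not reproduce Table 2.

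**Standard error.** SE = √{v × [ICC/8 + (1 − ICC)/1200]}, with v = p₁(1 − p₁) + p₂(1 − p₂). This is the same as a design effect of 1 + 149 × ICC.

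- Diet: v = 0.68 × 0.32 + 0.87 × 0.13 = 0.3307. The bracket is 0.012875 + 0.000748 = 0.013623. SE = 0.0671; effect/SE = 0.190/0.0671 = 2.83. Design effect 16.35.
- Breastfeeding: v = 0.716 × 0.284 + 0.887 × 0.113 = 0.3036. The bracket is 0.011250 + 0.000758 = 0.012008. SE = 0.0604; effect/SE = 0.171/0.0604 = 2.83. Design effect 14.41.

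**Reproducing the plan.** Normal-reference power is Φ(2.83 − 1.96) ≈ 0.81 in both rows. With a pooled variance it is 0.787 (diet) and 0.790 (breastfeeding). Table 2's 0.80 is therefore recovered, to rounding, with a two-sided normal test.

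**Where the variance lies.** The between-facility share is (ICC/8) divided by the bracket: 0.012875/0.013623 = 0.945 and 0.011250/0.012008 = 0.937. The df for an unadjusted comparison are thus essentially 16 − 2 = 14.

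**Same effect and SE, t on 14 df** (critical value 2.145, noncentral t):

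| | Diet | Breastfeeding |
|---|---|---|
| Power stated | 0.80 | 0.80 |
| Power, t(14) | 0.749 | 0.750 |
| Planned difference | 19.0 pp | 17.1 pp |
| Difference detectable at 80%, t(14) | 20.0 pp | 18.0 pp |
| Power with unlimited clients per facility, t(14) | 0.773 | 0.777 |

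A beta-binomial simulation with 8 + 8 facilities of 150 gives t(14) power of about 0.75 in both rows, in agreement.

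**If 1.96 is used on a 14-df variance.** True two-sided size = 2 × P(T₁₄ > 1.96) = 0.070.

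**Sensitivity to the ICC.** Power on 14 df returns to 80% at an ICC of 0.090 (diet) or 0.079 (breastfeeding), about 12% lower than planned. An ICC 10% lower gives 0.79; 10% higher gives 0.71.

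**What baseline adjustment would have to do.** One facility-level covariate leaves 13 df. Power is 80% if it removes about 14% of the between-facility variance, a baseline-endline facility correlation of √0.135 ≈ 0.37 with the slope known. With the slope estimated, and baseline counts of "1200 in intervention and 200 in control groups" spread evenly (150 and 25 per facility), simulated power at assumed correlations of 0, 0.37, 0.5 and 0.6 is about 0.71, 0.76, 0.80 and 0.84.

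**If the matching is analysed as 8 pairs.** 7 df gives about 0.68 in both rows, with no gain from matching.

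**The case against.** The strongest reply is that the planned test is ANCOVA, not the unadjusted endline comparison evaluated here, and that adjustment may recover five points. That stands as a possibility. But Table 2 claims its 80% without any such gain, no correlation is given anywhere, and the comparison group's baseline is thin. With an estimated slope the correlation would have to be near 0.5. A reader might infer that the planned ANCOVA itself has 75% power; the documents do not support that, because its power cannot be computed from them. The same holds for the counselling scores that section 10 lists as an indicator, since Table 2 sizes binary items only.

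A second reply is that the gap is small beside the uncertainty in the ICC. That is fair. Even the source of the ICCs is unclear: section 7 attributes them to the baseline assessment, while footnote 1 to Table 2 reads "Data from AINNS study [8]". The missing df rule remains at any ICC.

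A reader might also put power as low as 73%, by using the pooled variance with t on 14 df. That applies a null variance to power under the alternative and disagrees with the simulation, so 75% is the supportable figure.

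Nor does fixing 14 df by itself secure 5%. Section 1 describes the comparison facilities as matched, and sections 1 and 6 place the facilities of each group within two NGOs. Either feature, if reflected in the analysis, leaves fewer df.

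**Conclusion.** The concern holds for the two counselling-quality rows. On the plan's own unadjusted inputs, 80% power and a 5% level do not hold together: a test that holds 5% on 14 df has about 75% power and misses the planned effect about one time in four, not one in five. More clients in the same facilities would not close the gap. This rests on Table 2's ICCs, equal cluster sizes, a two-sided test, no NGO-level variance and no gain from baseline adjustment.

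Two further inferences go too far. The documents do not say that a 1.96 cutoff will be used, so the 7% size is what would follow if it were, not an established property of the trial. And the three behaviour rows should not be read as either deficient or safe. At 800 per group their t(14) power is about 0.93 (IFA), 0.88 (dietary diversity) and 0.81 (early initiation), so they fall outside this point only if all 800 clients contribute to each outcome. Section 7 says the ANC and child samples will be pooled, but Table 4 splits interviews into 400 and 400 per group. At 400 the figures would be about 0.70, 0.73 and 0.70.

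**What to change.** In section 10, require a small-sample reference on between-facility df for all client-level impact tests. Examples are REML with Kenward-Roger or Satterthwaite df for continuous counselling scores, and a facility-level summary analysis for binary outcomes. State and justify the df: at most 14 unadjusted and 13 with one facility-level covariate, and fewer if the matching is analysed as pairs (7 df) or if NGO-level variance is allowed for.

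In Table 2, restate the two quality rows as about 75% power at 19.0 and 17.1 pp, or about 20 and 18 pp detectable at 80%, before any gain from baseline adjustment. If such a gain is relied on, state the baseline-endline facility correlation assumed.

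The cost is a short paragraph and two table rows, with no new data. Intervals become about 9% wider at 14 df (2.145/1.96) and 10% wider at 13 df (2.160/1.96), before any gain from ANCOVA. The document is dated October 2021 and its endline timeline puts data collection in May-June 2022, so on that schedule the rule could be set before endline data exist.

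### Section 10 names analysis of covariance with a facility random effect, but the rounds are separate cross-sections: the covariate and the two-round error structure are undefined, and no available reading is adequate.

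*Combined protocol and SAP*

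**What the plan says.** Section 10 (Analysis plan): "Impacts on these outcomes will be estimated using analysis of covariance which is an accepted impact evaluation analysis approach that is widely used". The clustering provision for impacts is "Further adjustment for geographic clustering at the facility level will be done using random effects". No covariate, model equation, round term, arm-by-round term or degrees-of-freedom rule is given.

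Section 7 (Sample size) sets the target as a difference "between intervention and comparison groups in the changes over time for different context-specific outcomes".

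Section 8 recruits, in each round, women currently attending for antenatal care and mothers of children under 12 months. The only planned re-contact is the home interview within the same round. The timelines in Section 11 put baseline fieldwork in October-November 2019 (comparison) and January-February 2020 (intervention), and endline data collection in May-June 2022.

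On baseline size, Section 9.3 reports that "1400 case observations (1200 in intervention and 200 in control groups) were conducted". Endline plans 1200 in each group.

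**The concern.** With 27 to 32 months between rounds and eligibility tied to current pregnancy or a child under 12 months, the rounds are in effect different people. The documents do not say so in one sentence, but no linkage is planned and eligibility makes it a secure inference. Analysis of covariance therefore has no client-level baseline value to adjust for, and the analyst must choose among:

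- (a) pooling both rounds with a facility random intercept;
- (b) using the facility's baseline mean as covariate;
- (c) comparing endline only, perhaps adjusted for client characteristics.

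These give materially different inference. The groups are not randomised and are run by different NGOs, so a baseline gap is plausible. At stake are the standard errors for counselling quality, a primary outcome, and the control of baseline differences for every client-level impact.

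**Working it through.** **Inputs.** From Table 2: diet counselling 68.0% v 87.0%, ICC 0.103; breastfeeding counselling 71.6% v 88.7%, ICC 0.09; 100+ IFA 54.5% v 64.0%, ICC 0.001; dietary diversity 74.0% v 83.5%, ICC 0.009; early initiation 32.8% v 46.3%, ICC 0.024. There are 8 facilities per arm. Case observations (Section 9.3): baseline 1200 and 200, endline 1200 and 1200, so 150 v 25 per facility at baseline. Client interviews (Table 4), per client type: baseline 400 and 70, endline 400 and 400, so 50 v 8.75 per facility at baseline. Assumed: r, the correlation of a facility's underlying level between rounds, is not in the documents and is varied from 0 to 1. Tests are taken as two-sided.

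**1. The plan's own figure.** The two-proportion formula needs 75 (diet) and 85 (breastfeeding) per group without clustering. Design effects 1 + 149 × ICC are 16.347 and 14.41, giving 75 × 16.347 = 1226 and 85 × 14.41 = 1225. This reproduces the 1200, but as an endline-only comparison with no change term.

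**2. Reading (a).** Work in units of p(1−p), with S = 3/1200 + 1/200 = 0.0075. The stable facility part cancels from the arm-by-round contrast.

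- True variance = 4·ICC·(1−r)/8 + (1−ICC)·S.
- Reported variance with an intercept only = (1−ICC·r)·S.

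Diet at r = 0.8:

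- True: 0.0103 + 0.0067275 = 0.0170, so SE = √(0.2176 × 0.0170) = 6.1 pp.
- Reported: 0.9176 × 0.0075 = 0.00688, so SE = 3.9 pp.
- The ratio is 1.57, and the false-positive rate 2[1 − Φ(1.96/1.57)] is about 21%.

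| r | true SE (pp) | reported SE (pp) | false positives, formula | simulated |
|---|---|---|---|---|
| 1 | 3.8 | 3.8 | 5% | 5% |
| 0.9 | 5.1 | 3.8 | 14% | 15% |
| 0.8 | 6.1 | 3.9 | 21% | 21% |
| 0.5 | 8.4 | 3.9 | 36% | 36% |
| 0 | 11.3 | 4.0 | 48% | 50% |

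The simulation used binary data with these cell sizes, a pooled random-intercept model and a z test, 1500 runs per setting. Other cases from the same formula:

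- Breastfeeding counselling: 13%, 19% and 33% at r = 0.9, 0.8 and 0.5.
- Diet, one visit type only (S = 0.015): about 9%, 14% and 24%.
- Behaviours, interviews with client types together (S = 3/800 + 1/140), r = 0.8 to 0.5: about 5% (IFA), 6-7% (dietary diversity) and 8-12% (early initiation).

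**3. Reading (b).** Expected slope on the facility baseline mean = 2·ICC·r / [2·ICC + (1−ICC)/m_int + (1−ICC)/m_comp]. One minus the slope is the share of a stable gap left in the effect, judged against parallel trends.

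- Diet, r = 1: 0.206/(0.206 + 0.00598 + 0.03588) = 0.83, so 17% stays. At r = 0.8 about 34% stays.
- Breastfeeding, r = 1: 19%.
- One visit type (75 v 12.5), r = 1: 29% (diet) and 32% (breastfeeding).
- Behaviours by client type (50 v 8.75), r = 1: 73% (early initiation), 88% (dietary diversity) and over 98% (IFA).

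Simulating diet counselling with a stable 10-pp gap left 1.9, 2.4, 3.4 and 5.4 pp in the estimate at r = 1, 0.9, 0.8 and 0.5. With no gap, the false-positive rate was 4-6% using t.

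**4. Reading (c).** All of any baseline gap stays. The simulated 10-pp gap gave 20-23% false positives with a t test. With no gap, z in place of t on 14 df gives about 7%.

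**5. The alternative.** A comparison of the 8 v 8 facility changes (Welch t) gave 4-6% false positives at every r with no gap, and 3-6% with the 10-pp gap.

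Power uses Table 2 effects, the true variance above at the control proportion, and t on 14 df:

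- Diet: 19/6.1 pp gives about 83% at r = 0.8; 19/8.4 pp gives 56% at r = 0.5.
- By client type at Table 4 sizes (S = 3/400 + 1/70), r = 0.5 to 0.8: about 22% for IFA, 26-27% for dietary diversity and 37-41% for early initiation.

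**The case against.** The strongest reply is that Section 10 never says the rounds are pooled, nor that a facility mean is the covariate. An endline comparison with client covariates fits the text, and Table 2 is laid out and sized that way, with a footnote assuming no control-group change. On that reading neither the (a) nor the (b) figures apply. This stands as a limit on the claim. It does not rescue the plan, because an endline contrast is not the change that Section 7 targets and leaves any baseline gap in place.

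A reader might infer that the plan carries a 20-40% false-positive rate. The documents do not support that. It needs r of roughly 0.4 to 0.8 with visit types analysed together, and nothing fixes r. Two years spanning COVID, and the staff turnover and disrupted training in Table 1, argue against r near 1 but do not supply a value.

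A reader might also infer that analysis of covariance is unsound in any form. It is not. With a facility-mean covariate most of a stable gap is removed for pooled counselling outcomes when r is high, and error is near nominal when there is no gap.

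The behaviour shares in (b) are fractions of an unstated gap. If facilities vary only as Table 2's ICCs imply, the SD of the 8 v 8 gap, √[2·ICC·p(1−p)/8], is about 0.8 pp (IFA), 2.1 pp (dietary diversity) and 3.6 pp (early initiation), against expected effects of 9.5 to 13.5 pp. Non-randomised groups may differ by more, but no figure is given. Section 10 also names counselling scores, for which there is no ICC; the calculations use Table 2's binary rows.

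**Conclusion.** The point holds as a defect of specification with real consequences. Section 10 has no client-level covariate for its named method and no term that delivers Section 7's difference in changes. Each available reading either understates the standard error (a), leaves part of a stable baseline gap in the effect (b), or leaves all of it (c).

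The error-rate problem under (a) is material for counselling quality: 5% to about 50% over the full range of r, and 14% to 36% for diet at r from 0.9 to 0.5 with visit types pooled. It is minor for the low-ICC behaviours. The adjustment problem under (b) runs the other way: modest for pooled counselling if facility levels persist, near-complete for behaviours.

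The sizes rest on Table 2's ICCs, equal variance across rounds, the planned cell sizes and an assumed r. The bias figures also take parallel trends as the standard.

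**What to change.** In Section 10, name one main analysis for counselling quality: a two-round model with arm, round, arm-by-round, a facility random intercept and a facility-by-round random effect. A comparison of the 8 versus 8 facility-level changes is an acceptable equivalent. Specify small-sample degrees of freedom for 16 facilities. Report any model using the facility baseline mean as a sensitivity analysis, and state its covariate. For behaviour outcomes, print the endline-only contrast beside the two-round estimate.

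This needs text and one variance term, and no new data. The cost is precision: intervals widen, and the small comparison baseline (200 observations, 70 interviews per client type) enters the contrast at full weight. The power figures in step 5 of the working should be stated in Section 7, with r shown as an assumption, so that a null result on the behaviours is not over-read.
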